9.4.4 Safety Analyses

Adverse events will be coded as per the Common Terminology Criteria for Adverse Events (CTCAE) Version 5.0 and each AE will be counted once only for a given participant. The

severity, frequency, and relationship of AEs to study intervention will be presented by System Organ Class (SOC) and preferred term groupings. Each AE reported will include start date, stop date, severity, relationship, expectedness, outcome, and duration. Adverse events leading to premature discontinuation from the study intervention and serious treatment-emergent AEs will be presented in a separate table.

9.4.5 Baseline Descriptive Statistics

Descriptive statistics will be provided to summarize the characteristics of the participants at baseline.

9.4.6 Planned Interim Analyses

There is no planned interim analysis for this study.

9.4.7 Sub-Group Analyses

Due to small sample size and because this is a proof-of-principle study, primary and secondary endpoints will not be analyzed based on age, sex, race/ethnicity, or other demographic characteristics. Primary and secondary endpoints will be analyzed in each of the analysis populations listed in Section 9.3.

9.4.8 Tabulation of individual Participant Data

Individual participant data may be presented descriptively or graphically over time.

9.4.9 Exploratory Analyses

The pharmacodynamics variables will be analyzed in different analysis populations. Potentially linear mixed effects models may be used to analyze the repeated measures data if assumptions warrant.

10 REGULATORY AND OPERATIONAL CONSIDERATIONS

10.1 Informed Consent Process

10.1.1 Consent Procedures and Documentation

Standard Consent Procedures: The informed consent document will be provided as a physical or electronic document to the subject or consent designee(s) as applicable for review prior to consenting. A designated study investigator will carefully explain, either in-person or remotely (e.g., via telephone or other NIH approved remote platforms used in compliance with policy, including HRPP Policy 303) the procedures and tests involved in this study, and the associated risks, discomforts, and benefits. In order to minimize potential coercion, as much time as is needed to review the document will be given, including an opportunity to discuss it with friends, family members and/or other advisors, and to ask questions of any designated study investigator. A signed informed consent document will be obtained prior to entry onto the study.

The initial consent process as well as re-consent, when required, may take place in person or remotely (e.g., via telephone or other NIH approved remote platforms used in compliance with policy, including HRPP Policy 303) per discretion of the designated study investigator and with the agreement of the subject/consent designee(s). Whether in person or remote, the privacy of the subject will be maintained. When in person, consenting investigators and subject/consent designee, will be located in a private area (e.g., clinic consult room or private

inpatient room). When consent is conducted remotely, the subject/consent designee will be informed of the private nature of the discussion and will be encouraged to relocate to a more private setting if needed. If consent is obtained remotely, participants and investigators will view individual copies of the approved consent document at their respective locations.

For electronic consent: The study team will confirm with the participant that they are comfortable using the electronic consenting before proceeding with obtaining consent. If not, other methods will be utilized. When an electronic document with a digital signature is used for the documentation of consent, this study will use the iMedConsent™ platform which is 21 CFR, Part 11 compliant to obtain the required signatures. During the consent process, participants/LARs and investigators will view the same approved consent document simultaneously in their respective locations. The identity of the participant will be determined by verifying a government issued identification card via the telehealth platform, prior to obtaining the signature. iMedConsent will capture electronic signatures via the methods listed below:

- Using a smartphone: participants will be registering their signatures using their finger.

Participants will receive a secure link that leads them to secure “web pages” that will capture their electronic signatures using their finger.

- Using a computer/tablet/laptop: participants will be registering their signatures using a computer mouse or their finger/stylus (for touch/stylus enabled tablets and computer screens).

Participants will receive a secure link that leads them to secure “web pages” that will capture their electronic signatures using the aforementioned methods. Once the completed consent has been saved, it will post to CRIS within a few minutes. All consents completed in iMedConsent™ will post to both the Documents tab and the Consents tab in CRIS. If the research participant has a FollowMyHealth™ account a copy of the completed consent will be posted to their account within two business days. The study team will provide the research participant with a printed copy of the signed document.

10.1.2 Consent for minors when they reach the age of majority

Not applicable.

10.1.3 Considerations for Consent of NIH staff, or family members of study team members

Consent for NIH staff will be obtained as detailed above with following additional protections:

Consent from staff members will be obtained by an individual independent of the staff member’s team whenever possible. Otherwise, the consent procedure will be independently monitored by the CC Department of Bioethics Consultation Service in order to minimize the risk of undue pressure on the staff member.

10.1.4 Consent of Participants who are, or become, decisionally impaired

Adults unable to provide consent are excluded from enrolling in the protocol. However, it is possible that participants enrolled in the protocol may permanently lose the capacity to consent for themselves during the course of this study. In the event this occurs, the participants will be withdrawn from the study.

10.2 Study Discontinuation and Closure

This study may be temporarily suspended or prematurely terminated if there is sufficient reasonable cause. Written notification, documenting the reason for study suspension or termination, will be provided by the suspending or terminating party to study participants, investigator, funding agency, the Investigational New Drug (IND) sponsor and regulatory authorities. If the study is prematurely terminated or suspended, the Principal Investigator (PI) will promptly inform study participants, the Institutional Review Board (IRB), and sponsor and will provide the reason(s) for the termination or suspension. Study participants will be contacted, as applicable, and be informed of changes to study visit schedule and encaleret discontinuation procedures.

If a participant experiences severely symptomatic hypocalcemia (e.g., seizures, QTcF > 500 ms, IV calcium requirement) during the study, or severely symptomatic hypercalcemia (e.g., lethargy/stupor), recruitment will be paused and the DSMC will be consulted. At that time the DSMC will review the data to determine whether there is sufficient cause to terminate the study. The investigators may additionally propose amendments to the protocol to prevent recurrence of the event.

If three participants experience a Grade 3 or greater adverse event that is related to study treatment, recruitment will be paused and the DSMC will be consulted. At that time the DSMC will review the data to determine whether there is sufficient cause to terminate the study.

Additional circumstances that may warrant termination or suspension include, but are not limited to:

- Determination of unexpected, significant, or unacceptable risk to participants
- Demonstration of efficacy that would warrant stopping
- Insufficient compliance to protocol requirements
- Data that are not sufficiently complete and/or evaluable
- Determination that the primary endpoint has been met
- Determination of futility

Study may resume once concerns about safety, protocol compliance, and data quality are addressed, and satisfy the sponsor, IRB and the Food and Drug Administration (FDA).

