4.3 Justification for Dose

The current study proposes to initiate first-in-patient dosing in the new target population of participants with PSH with encaleret 162 mg BID over a 5-day inpatient admission.

Twice a day dosing is necessary to maximize and sustain the effect on renal calcium excretion. In previous studies in euparathyroid patients, once daily dosing did not normalize 24-hour urinary calcium excretion, however, calcium excretion was suppressed for the first 12 hours. In the ongoing Phase 2B study of patients with ADH1 due to activating CASR mutations, encaleret needed to be given twice daily to maintain 24-hour effects on blood and urine calcium.

The present PSH cohort is expected to be protected from hypercalcemia experienced by previous cohorts on encaleret (normal controls or patients with osteoporosis or ADH1). This is because patients with PSH, who have insufficient parathyroid tissue, are unlikely to have a robust PTH response to encaleret. On the other hand, because of the lack of functional parathyroids in this patient population, these patients may be at increased risk of symptomatic hypocalcemia during the course of the study. Thus, maximizing the encaleret dose in this population is both important for the safety of the patients, to reduce risk of hypocalcemia, as well as increasing the probability of establishing a definitive proof-of-principle which is the goal of this study.

A primary concern in this proof-of-principle study is to not make a type 2 error (not see an effect when one exists). Thus, we chose the highest dose that has been safely used previously in patients with hypoparathyroidism/ADH1 to increase the likelihood that we will see our predicted effect.

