8.3.7 Serious Adverse Event Reporting

In consultation with the PI, a trained member of the study team will be responsible for conducting an evaluation of all adverse events and shall report the results of such evaluation to the NIH Institutional Review Board (IRB) as per [Policy 801](#). All SAEs will be reported to the DSMC at routine intervals or as indicated by the DSMC.

All SAEs, whether or not considered study intervention related, will be reported to the NIDCR Office of the Clinical Director within 7 days of investigator awareness. The study sponsor will be responsible for notifying the Food and Drug Administration (FDA) of any unexpected fatal or life-threatening suspected adverse reaction as soon as possible, but in no case later than 7 calendar days after the sponsor's initial receipt of the information. In addition, the sponsor must notify FDA and all participating investigators in an Investigational New Drug (IND) safety report of potential serious risks, from clinical trials or any other source, as soon as possible, but in no case later than 15 calendar days after the sponsor determines that the information qualifies for reporting.

All SAEs will also be reported to Calcilytix within 1 business day in order that Calcilytix may fulfill cross reporting requirements to the Calcilytix IND and all participating investigators under the IND (21 CFR 312.32(c)(1)).

All serious adverse events (SAEs) will be followed until satisfactory resolution or until the site investigator deems the event to be chronic or the participant is stable.

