8.3.9 Events of Special Interest

Hypocalcemia in PSH

Hypocalcemia is not an expected side-effect of treatment with encaleret, but it is a complication of the underlying disease being treated. As such, hypocalcemia may develop whenever the underlying disease is inadequately treated and might occur due to either inadequate or missed doses of a specific, effective medication.

The current study involves reducing the dose of current maintenance medications or suspending their use entirely (i.e., oral calcium supplements and calcitriol), to facilitate evaluation of encaleret and potentially establishing clinical proof-of-principle. Under these circumstances there is a risk that participants could experience symptoms of hypocalcemia prior to reaching encaleret maximal effect. In order to mitigate this risk, the study design emphasizes safety foremost. All changes to oral maintenance medications in conjunction with encaleret dosing will be conducted with participants in residence at the Clinical Center, with multiple daily measurements of blood calcium and close supervision by health professionals with experience caring for individuals with hypoparathyroidism. In addition to these precautions, monitoring for and capture of events suggestive of or consistent with hypocalcemia will be reviewed as an AE of special interest as described below.

Adverse Events of Hypocalcemia: Symptomatic and Asymptomatic

Adverse events consistent with hypocalcemia will be classified as either symptomatic or asymptomatic, and assessed for severity, recognizing that there is a spectrum of clinical manifestations. Symptomatic hypocalcemia will be based on identification of new or worsening symptoms consistent with hypocalcemia such as numbness/tingling of hands, feet

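### The three-participant pause rule in Section 10.2 does not separate fatal or life-threatening related events from Grade 3 events, so one or two of them outside the calcium trigger force no pause or DSMC consultation

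*Combined protocol and SAP*

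**What the plan says.** Section 10.2 (Study Discontinuation and Closure) sets two numeric triggers. Both lead to a recruitment pause and DSMC consultation.

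- **Calcium trigger, one participant.** It begins "If a participant experiences severely symptomatic hypocalcemia (e.g., seizures, QTcF > 500 ms, IV calcium requirement) during the study" and extends to severely symptomatic hypercalcemia. Relatedness to encaleret is not required.
- **General trigger, three participants.** "If three participants experience a Grade 3 or greater adverse event that is related to study treatment, recruitment will be paused". Relatedness is required. Grades 3, 4 and 5 are counted alike.

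The other grounds in Section 10.2 are permissive: "Additional circumstances that may warrant termination or suspension include, but are not limited to". The closest to this point is "Determination of unexpected, significant, or unacceptable risk to participants".

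On routing, Section 8.3.7 says "All SAEs will be reported to the DSMC at routine intervals or as indicated by the DSMC". The same section sends all SAEs to the NIDCR Office of the Clinical Director within 7 days and to the manufacturer within 1 business day. The sponsor must notify the FDA of any "unexpected fatal or life-threatening suspected adverse reaction as soon as possible, but in no case later than 7 calendar days". Section 10.5 adds an independent medical monitor, an independent study monitor and DSMC meetings at intervals. Section 9.4.6 plans no interim analysis.

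**The concern.** The general trigger is a single count over a very wide range of severity. A participant with a related Grade 3 laboratory abnormality and a participant who dies of a related event each add one to the count. One episode needing IV calcium forces DSMC consultation; one related death of another kind does not, and neither does a second.

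The study treats at most 15 participants (Section 4.1), so three is 20% of the maximum sample. Section 4.3 describes the dose as the highest safely used before in hypoparathyroidism/ADH1 and the population as new. In that setting a fatal or life-threatening event judged related to the drug is the signal for which prompt independent review matters most. The plan leaves that review to discretion or to the next routine DSMC meeting.

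**Working it through.** The documents give no operating characteristics for the pause rule, so there is no stated figure to reproduce. The check has three parts.

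**1. The rule applied to cases**

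| Case | Mandatory pause and DSMC consultation? |
|---|---|
| One participant needs IV calcium for severely symptomatic hypocalcemia | Yes, calcium trigger |
| One death or life-threatening event caused by severe calcium disturbance | Yes, calcium trigger |
| One related death, other cause | No (1 < 3) |
| Two related deaths or life-threatening events, other cause | No (2 < 3) |
| Two of these plus a related Grade 3 event in a third participant | Yes, general trigger |

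**2. How often such events would stay under the count**

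Inputs: n = 15 treated (Section 4.1). The per-participant rate p of related fatal or life-threatening events not due to calcium disturbance is not in the documents. It is an assumption, taken from 2% to 20%.

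Formulas, with X binomial(15, p):
- P(X ≥ 1) = 1 − (1 − p)^15
- P(X ≥ 2) = P(X ≥ 1) − 15p(1 − p)^14
- P(X ≥ 3) = P(X ≥ 2) − 105p²(1 − p)^13

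At p = 5%:
- P(X ≥ 1) = 1 − 0.463 = 0.537
- P(X ≥ 2) = 0.537 − 0.366 = 0.171
- P(X ≥ 3) = 0.171 − 0.135 = 0.036

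| Assumed p | P(≥1) | P(≥2) | P(≥3) | Below three, given at least one |
|---|---|---|---|---|
| 2% | 26% | 4% | 0.3% | 99% |
| 5% | 54% | 17% | 4% | 93% |
| 10% | 79% | 45% | 18% | 77% |
| 20% | 97% | 83% | 60% | 38% |

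The P(≥3) column counts these events alone. Related Grade 3 events also count, so it is a lower bound on the probability that the rule fires. For example, if a further 10% of participants had a related Grade 3 event (also an assumption), a 10% rate would become 20% for the rule, and P(≥3) would rise from 18% to 60%.

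**3. How many more would be dosed after a first event**

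Assume sequential dosing and count participants dosed after the first such event until the third event or the end of dosing. Section 2.3.1 reports six PSH participants already exposed to encaleret. If they belong to this trial, which the text does not state, at most 15 − 6 = 9 remain. Given at least one event among those nine, the expected number dosed afterwards is 4.3, 4.5 and 4.8 at rates of 5%, 10% and 20%. These figures again ignore Grade 3 events, which could bring the pause earlier.

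**The case against.** **The calcium trigger is strict on purpose.** Section 8.3.9 does say "Hypocalcemia is not an expected side-effect of treatment with encaleret", and a reader might infer that the protocol is strictest where the drug is least suspect. The same sentence goes on to attribute hypocalcemia to the underlying disease. The section also explains that maintenance therapy is reduced or suspended, and Section 2.3.3 names calcium disturbance as the main known risk. A one-participant trigger for the chief foreseeable hazard is sensible. This stands: the calcium trigger is not at fault, and the two triggers do not contradict each other.

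**A related death would not go unseen.** It would reach the Clinical Director's office, the manufacturer and, if unexpected, the FDA within days. A medical monitor is in place, suspension for unacceptable risk is an express option, and IRB reporting follows a policy that is not reproduced. All of this stands, and a reader should not infer that such events escape oversight. What is missing is narrower: none of these routes obliges a pause or an event-triggered DSMC review.

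**The events may be rare.** Section 2.3.1 reports no serious or severe adverse events in 13 ADH1 patients at doses up to 171 mg BID. That is reassuring but weak: at a true 10% rate, 13 patients would show none with probability 0.9^13 = 25%. At 2%, two or more such events among 15 have only a 4% chance. Rarity also makes a stricter trigger cheap.

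**This is not strictly a first exposure.** Section 4.3 says "The current study proposes to initiate first-in-patient dosing in the new target population of participants with PSH", but Section 2.3.1 already reports six exposed PSH participants. The point does not depend on this being the first dosing in PSH.

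**Conclusion.** The point holds as a gap in the general trigger. Followed literally, Section 10.2 forces no pause and no DSMC consultation after one or two related fatal or life-threatening events outside the calcium trigger, provided that no other participant brings the related Grade 3-or-greater count to three.

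The size depends on an event rate that the documents do not give. With 15 treated, at least one such event has probability 26% to 97% over assumed rates of 2% to 20%; three or more has probability 0.3% to 60%. Two stronger readings are not supported:

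- The three-or-more figures are not the probability that the rule fires, because Grade 3 events are left out.
- It is not true at every plausible rate that dosing would usually finish first. At 20% the count reaches three 60% of the time on these events alone.

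The scale is also unsettled. Treating life-threatening and fatal events as grades above 3 relies on CTCAE version 5.0, which Section 9.4.4 names only for coding. Section 8.3.3 has investigators record mild, moderate or severe, without numbered grades, and Section 8.3.2 treats death as an outcome rather than an event.

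This is a worthwhile correction to the oversight rules. It does not bear on the efficacy analysis.

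**What to change.** In Section 10.2, the sponsor and DSMC should reconcile the two triggers so that a related fatal or life-threatening event does not face a looser automatic pause-and-consult trigger than a severe calcium event. The three-participant count can stay for Grade 3 events. The exact wording and count for the more severe events are for the sponsor and DSMC to set.

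The section should also state which severity scale Grade refers to, how it maps to the mild/moderate/severe record in Section 8.3.3, and that the event causing a death counts. Section 8.3.7 should then carry a matching route to the DSMC, so that it agrees with Section 10.2.

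The cost is a few sentences by amendment. The downside is a possible short recruitment pause while the DSMC reviews a single event.

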10.3 Confidentiality and Privacy

Participant confidentiality and privacy is strictly held in trust by the participating investigators, their staff, and the sponsor(s). This confidentiality is extended to cover testing of biological samples and genetic tests in addition to the clinical information relating to participants. Therefore, the study protocol, documentation, data, and all other information generated will be held in strict confidence. No information concerning the study or the data will be released to any unauthorized third party without prior written approval of the sponsor.

All research activities will be conducted in as private a setting as possible.

The study monitor, other authorized representatives of the sponsor, representatives of the Institutional Review Board (IRB), and/or regulatory agencies may inspect all documents and records required to be maintained by the investigator, including but not limited to, medical

records (office, clinic, or hospital) and pharmacy records for the participants in this study. The clinical study site will permit access to such records.

All participants' records will only be identified by subject number. The investigator will keep a master subject list on which the subject number and the full name, address, and telephone number of each subject are listed. The subject's contact information will be securely stored at NIH Clinical Center for internal use during the study. At the end of the study, all records will continue to be kept in a secure location for as long a period as dictated by the reviewing IRB, Institutional policies, or the Sponsor requirements.

Data collection will involve the use of a 21 CFR part 11 compliant EDC system, only authorized personnel will have access to the EDC system. All data collected in the context of this study will be stored in a secure location and evaluated according to regulatory requirements and applicable guidance for electronic records. Data will be stored and evaluated in such a way as to guarantee subject confidentiality in accordance with the legal stipulations applying to confidentiality of data. Study records (e.g., copies of CRFs, regulatory documents) will be retained at the NIH Clinical Center, along with adequate source documentation, according to local regulatory requirements and ICH requirements.

The investigator must retain a copy of all records that support CRFs for this study (e.g., ICFs, clinical laboratory reports, source documents, drug dispensing records) for a period of at least 15 years after study completion unless local regulations or NIH Clinical Center policies require a longer retention period.

If the investigator retires, relocates, or for other reasons withdraws from the responsibility of keeping the study records, custody must be transferred to a suitable alternate custodian employee of the study center or to a suitably qualified and responsible third party.

To further protect the privacy of study participants, a Certificate of Confidentiality has been issued by the National Institutes of Health (NIH). This certificate protects identifiable research information from forced disclosure. It allows the investigator and others who have access to research records to refuse to disclose identifying information on research participation in any civil, criminal, administrative, legislative, or other proceeding, whether at the federal, state, or local level. By protecting researchers and institutions from being compelled to disclose information that would identify research participants, Certificates of Confidentiality help achieve the research objectives and promote participation in studies by helping assure confidentiality and privacy to participants.

